### 16.3 Analysis Sets

The efficacy and safety analysis sets are defined as follows:

- **As-Treated (AT) Analysis Set:** This analysis set includes all patients who took part of any dose of study treatment, will be used as basis for the evaluation of antitumor effects and safety analyses. All analyses using this population will be based on the treatment actually received.
- **PK Analysis Set\*:** All patients in the AT analysis set who receive any amount of their assigned dose of the IMPs, Sym004, futuximab or modotuximab, have a measurable concentration of at least one of the IMPs for at least one timepoint after the first dose, with no significant protocol deviations that may impact the data.

**\*As of Amendment 5:** PK analysis will not be performed, therefore the PK analysis set is no longer applicable.

## 16.4 Trial Endpoints

**As of Amendment 5:** Due to the Sponsor’s decision to discontinue the trial (effective 20Dec2018), only clinical safety-related analyses will be conducted. The pre-Amendment 5 efficacy and exploratory endpoints as detailed below are no longer valid and will not be analyzed.

### 16.4.1 Primary Efficacy Endpoint (omitted as of Amendment 5)

Percentage change from baseline in the sum of the diameter of tumors designated as target lesions, as documented at the EOC2 tumor assessment.

### 16.4.2 Exploratory Endpoints and Analyses (omitted as of Amendment 5)

#### 16.4.2.1 Pharmacokinetic Endpoints

The PK profile of the IMPs will be derived based on the concentration time curves after the first and the 8th infusion on Cycle 2, Day 22. For patients dosed with Sym004, the serum concentration of futuximab and modotuximab will be measured in separate bioanalytical assays. The Sym004 serum concentration is defined as the sum of futuximab and modotuximab serum concentrations measured in a sample. The bioanalytical assays used for Sym004 assessment will also be applied for measurement of serum concentrations of futuximab and modotuximab in the patients dosed with futuximab drug product and modotuximab drug product, respectively.

For all three IMPs, the  $C_{max}$ ,  $C_{EOI}$ ,  $C_{trough}$  and  $T_{max}$  will be derived from observed data while  $AUC_{inf}$ ,  $AUC_{0-168h}$ ,  $CL$ ,  $CL_{ss}$ ,  $V_d$ , and  $T_{1/2}$  will be estimated using non-compartmental methods and actual time points. For selected infusions during repeated dosing,  $C_{EOI}$  and/or  $C_{trough}$  (equivalent to the concentration at EOI and SOI, respectively) will be assessed.

Individual curves of serum concentration of the IMPs versus time after the first and 8th infusion will be presented on log- and linear scale for all patients in the PK population. Furthermore, peak and trough serum concentrations for the period from first dose to EOC2 and EOT, before and after cross-over to Sym004 will be presented on a linear scale individual plots as appropriate. In addition, mean concentration time curves will be presented on linear scale using nominal time point by cohort and trial part. All PK endpoints will be listed and summarized by trial part and cohort (**Table 8**).

Table 8: PK Endpoint, Definitions, and Derivations	
Symbol	Definition and Derivation
$AUC_{inf}$	Area under the concentration-time curve from start of infusion to infinity for the first dose
$AUC_{0-168h}$	Area under the Concentration-Time Curve from Start of Infusion up to 168 hours
$CL$	Clearance after the first dose
$CL_{ss}$	Clearance in steady state at the nominal 8 th infusion
$C_{EOI}$	Concentration at the end of infusion
$C_{max}$	Maximum concentration
$C_{trough}$	Observed trough concentration (i.e., concentration of IMP measured pre-infusion)
$T_{1/2}$	Terminal elimination half-life
$V_d$	Volume of Distribution During the Terminal Phase after the First Dose

### 16.4.2.2 Modeling of Pharmacokinetic and Pharmacodynamic Data

All data collected in this trial may be used for modeling of PK, tumor size, safety, and biomarker assessments. Preliminary data generated during the trial may be used for exploratory modelling. The final data, i.e., after database lock, will be used for the final model and potentially for cross-trial modelling. These modelling activities will be reported separately from the current trial.

## 16.5 Statistical Analysis

**As of Amendment 5:** Due to the Sponsor's decision to discontinue the trial (effective 20Dec2018), only data from clinical safety-related evaluations will be summarized. Since only 2 patients are being treated in the study, the available baseline and safety data for these two patients will be presented as either patient profiles or patient listings. The pre-Amendment 5 full statistical analysis as detailed below will not be performed.

### 16.5.1 General Specifications

Statistical analyses will be carried out using Statistical Analysis System (SAS®) Version 9.4 or higher.

The data cut-off for primary analysis date will be determined once all patients in the AT analysis set complete their first on-study tumor assessment.

In general, continuous variables will be summarized using descriptive statistics by reporting the number of observations, mean, standard deviation, median, minimum, and maximum; Categorical/discrete variables will be summarized using frequency distributions showing the number and percentage of patients within each category; unless otherwise specified.

Baseline is defined as the last available observation prior to the first administration of study drug on C1D1. If a baseline value is missing, no change from baseline will be calculated.

Unless indicated otherwise, summary statistics will be presented using observed data only. Missing data will not be imputed unless otherwise specified.

Data from all study sites will be pooled in the summaries if more than one site is involved in the study. Study sites will be identified in the data listings.

### 16.5.2 Patient Disposition and Baseline Characteristics

#### 16.5.2.1 Patient Disposition

Number of patients in each analysis set, reasons for exclusion, withdrawals of patients from study drug and reason, as well as withdrawal from study follow-up, will be summarized using frequency distributions. Randomization and/or stratification errors, if any, will be summarized.

#### 16.5.2.2 Baseline and Disease Characteristics

Patient demographics, baseline and disease characteristics such as age, sex, race, duration of metastatic disease, prior anti-cancer therapies, measurable/non-measurable disease, left or right colon, and ECOG PS, will be presented using descriptive statistics or frequency distributions, as appropriate.

### 16.5.3 Exposure

Exposure to study drug and the administration profile will be summarized descriptively for each treatment Arm with respect to duration of exposure, number of treatment cycles, cumulative dose, relative dose intensity, and dose modifications.

## 16.6 Primary Analysis

**As of Amendment 5:** Due to the Sponsor's decision to discontinue the trial (effective 20Dec2018), only clinical safety-related analyses will be conducted. The planned efficacy analyses as detailed below will not be performed.

### 16.6.1 Efficacy Analysis

Percentage change from baseline in the sum of the diameters of tumors designated as target lesions, as tumor volume documented at the EOC2 tumor assessment will be calculated and plotted by treatment Arm using Waterfall plots. Percent of patients with on-study tumor shrinkage will be presented along with the associated 95% CIs. Magnitude of tumor shrinkage will also be summarized by treatment Arm, as appropriate.

## 16.7 Secondary Analysis

### 16.7.1 Safety Analysis

The safety evaluations will focus on AEs and laboratory assessments. All patients included in the AT analysis set will be evaluated by treatment Arm in the safety analysis.

Adverse events will be coded according to the Medical Dictionary for Regulatory Activities (MedDRA) terminology and the severity of the toxicities will be graded according to the CTCAE v5, where applicable. Concomitant medications will be coded according to the World Health Organization (WHO) Medication Dictionary for Concomitant Medication.

All AEs will be summarized (incidence) and listed by the System Organ Class (SOC), preferred term, toxicity/severity grade, and causal relationship to study medication. In addition, separate summaries of SAEs and Grade 3 and 4 AEs will be presented.

Special attention will be paid to dermatologic toxicities, hypomagnesemia, hypocalcemia, hypokalemia, and IRRs.

Hematological and chemistry laboratory parameters will be graded according to the CTCAE v5 criteria, where applicable. Absolute values and changes from baseline will be summarized by cycle. The on-study worst severity grade will also be summarized. In addition, time to event (certain severity of selected laboratory tests), and time to resolution will also be summarized as appropriate.

Further safety analysis details will be provided in the SAP.

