Statistical Methods	
As of Amendment 5: Due to the Sponsor’s decision to discontinue the trial (effective 20Dec2018), only clinical safety-related analyses will be conducted. Planned efficacy analyses as detailed below will not be performed.
 
Analysis Sets
 
 
• As-Treated (AT) Analysis Set: This analysis set includes all patients who took part of any dose of study treatment, will be used as basis for the evaluation of antitumor effects and safety analyses. All analyses using this population will be based on the treatment actually received.
 
• PK Analysis Set*: All patients in the AT analysis set who receive any amount of their assigned dose of the IMPs (i.e., Sym004, futuximab, or modotuximab), and have a measurable concentration of at least one of the IMPs for at least one timepoint after the first dose, with no significant protocol deviations that may impact the data.
 
 
*As of Amendment 5: PK analysis will not be performed, therefore the PK analysis set is no longer applicable.
 
Primary Efficacy Analysis
 
Percentage change from baseline in the sum of the diameter of tumors designated as target lesions (per RECIST v1.1), as documented at the EOC2 tumor assessment will be calculated and plotted by treatment Arm using Waterfall plots. Percent of patients with on-study tumor shrinkage will be presented along with the associated 95% confidence intervals (CI). Magnitude of tumor shrinkage will also be summarized by treatment Arm, as appropriate.
 
Safety Analyses
 
The safety evaluations will focus on AEs and laboratory assessments. All patients included in the AT analysis set will be evaluated by treatment Arm in the safety analysis. Special attention will be paid to dermatologic toxicities, hypomagnesemia, hypocalcemia, hypokalemia, and IRRs.

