## 16.8 Exploratory Analysis

**As of Amendment 5:** Due to the Sponsor's decision to discontinue the trial (effective 20Dec2018), only clinical safety-related analyses will be conducted. The planned exploratory analyses as detailed below will not be performed.

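### Does the by-Arm wording left in Section 16.7.1 and the synopsis after Amendment 5 leave the safety analysis undecided?

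*Protocol*

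**What the plan says.** Amendment 5 reduces the trial to safety follow-up of two treated patients. The relevant statements in the protocol are these.

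- **Section 16.5 (Amendment 5 note).** For the two patients, "the available baseline and safety data for these two patients will be presented as either patient profiles or patient listings". The note goes on: "The pre-Amendment 5 full statistical analysis as detailed below will not be performed".
- **Section 16.7.1 (no Amendment 5 note).** "All patients included in the AT analysis set will be evaluated by treatment Arm in the safety analysis". It also keeps the incidence tables: "All AEs will be summarized (incidence) and listed by the System Organ Class (SOC), preferred term".
- **Synopsis, Statistical Methods.** The Amendment 5 note there cancels efficacy only: "Planned efficacy analyses as detailed below will not be performed". The by-Arm safety sentence follows unchanged, and profiles or listings are not mentioned.
- **Sections 16.6 and 16.8.** Each has its own cancelling note: "The planned efficacy analyses as detailed below will not be performed" and "The planned exploratory analyses as detailed below will not be performed". Section 16.10 has a similar one.
- **Section 16.3.** For the As-Treated set, "All analyses using this population will be based on the treatment actually received".
- **Sections 6.3.5 and 6.5.4.** Both patients were randomized to futuximab. The first received it and was switched to Sym004 at the end of Cycle 1. The second was given Sym004 instead of the randomized drug.

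**The concern.** Safety reporting is all that is left of this trial, and two parts of the protocol seem to describe it differently. One asks for individual profiles or listings. The other asks for evaluation by Arm with incidence summaries. The sections on either side of 16.7 were each given a note withdrawing their content and 16.7 was not, so a reader could take 16.7.1 to be the section left in force. The synopsis encourages that reading because it withdraws only efficacy.

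The second strand is the label for the first patient. Both futuximab and Sym004 are treatments that patient actually received, so the rule in 16.3 does not produce a single Arm. Section 2.4 describes this as the first clinical study of the two antibodies given singly, and that patient's first cycle is the only single-agent exposure in the trial. If by-Arm tables were built and the patient were counted under the last drug received, events that began on futuximab would appear as Sym004 events and the futuximab Arm would be empty.

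**Working it through.** The plan states no figure on this point to reproduce. The check is a reading of the sections against each other, followed by a count that shows what the label could change.

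**1. Which instruction governs.**

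- Section 16.5 is headed Statistical Analysis. Its note belongs to Amendment 5, refers expressly to these two patients, and names safety data.
- The text of 16.7.1 predates Amendment 5, is general, and stands after 16.5. It therefore falls within the full analysis, detailed below, that 16.5 withdraws.
- Section 3.1 withdraws the secondary objective, which was the safety comparison of Sym004 with the single agents. By-Arm tables would serve that comparison and no longer have a purpose.
- The notes in 16.6, 16.8 and 16.10 say that an analysis will not be done. The same note in 16.7 would be wrong, because safety data are still reported. The dictionary coding, severity grading and listing of adverse events in 16.7.1 remain usable for listings.
- The synopsis is less complete than 16.5 but does not forbid listings, and its safety paragraph does not itself call for incidence tables. A listing can be sorted by treatment.

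**2. What the label could change if by-Arm tables were produced.** There are two treated patients. Patient 1 had futuximab, then Sym004. Patient 2 had Sym004 only.

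| Rule for patient 1 | Arm A | Arm B | Arm C |
|---|---|---|---|
| As randomized (excluded by 16.3) | 0 | 2 | 0 |
| First drug received | 1 | 1 | 0 |
| Last drug received | 2 | 0 | 0 |
| Every drug received, by period | 2 | 1 | 0 |

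Section 16.3 settles patient 2 as Sym004 and removes the as-randomized row. It does not choose among the other three.

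Take one adverse event in patient 1 during the futuximab cycle and none in patient 2:

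- First drug: 1/1 = 100% in Arm B.
- Last drug: 1/2 = 50% in Arm A.

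Exact (Clopper-Pearson) 95% limits:

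- 1/1: lower limit solves p = 0.025, giving 2.5%; upper limit 100%.
- 1/2: lower limit solves 1 − (1 − p)² = 0.025, so p = 1 − √0.975 = 1.26%; by symmetry the upper limit is 98.74%.

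The plan does not ask for intervals on adverse event rates. They are given only to show that a by-Arm rate says nothing here, whichever label is used.

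**3. What happens under 16.5.** A profile or listing shows each event for a given patient and has no denominator, so none of the counts in step 2 is reported. The switch at the end of Cycle 1 is recorded in the protocol, and Section 6.5.4.5 requires infusion start and stop times in the CRF. Events can be placed before or after the first Sym004 dose if the listing carries onset dates. Section 10.2.1 does not name onset date among the items it spells out, so that is an assumption, though an ordinary one for adverse event collection.

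**The case for a change.** The strongest case for a change is as follows. Section 16.5 is a heading of the same rank as 16.6, 16.7 and 16.8 and has three subsections of its own, so what it calls below can be confined to those. If it reached further, the separate notes in 16.6, 16.8 and 16.10 would be superfluous. Those notes also say that only safety-related analyses will go ahead, which points to 16.7 as the survivor. The synopsis has no equivalent of the 16.5 sentence at all. And because the trial holds the only single-agent exposure, attribution of that patient's events should not depend on which section the report writer opens.

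Part of this stands. The synopsis and 16.7.1 were not aligned with 16.5, and treatment received does not give one Arm for the first patient. The rest carries less weight. Even if the reach of the cancelling sentence were disputed, the sentence before it in 16.5 assigns these patients' safety data to profiles or listings in terms, and that does not depend on what lies below. Superfluous notes are common when an amendment is inserted section by section. The last-drug label is also strained: a patient had not received Sym004 when a futuximab-cycle event began. How a listing marks the two periods is a layout matter, and Sections 16.1 and 16.7.1 leave listing templates and further safety detail to the SAP, which is not at hand.

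**Conclusion.** No change to the plan follows. The form of the safety report is settled by Section 16.5, and that form suits two patients. The unaligned wording in 16.7.1 and the synopsis is a clerical slip. The labelling question would alter a number only in by-Arm tables, which 16.5 removes; even there it would move one event between 1/1 and 1/2, neither of which supports any conclusion. There is no inference, the objectives are withdrawn, and Section 15.4 provides for an abbreviated report.

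This rests on two assumptions: that the analyst follows the specific Amendment 5 instruction over the older general text, and that the listings carry dates from which each event can be set against the switch from futuximab to Sym004. Both are normal practice. A cross-reference to 16.5 would tidy the text, but it would not change what is reported.

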## 16.8 Exploratory Analysis

**As of Amendment 5:** Due to the Sponsor's decision to discontinue the trial (effective 20Dec2018), only clinical safety-related analyses will be conducted. The planned exploratory analyses as detailed below will not be performed.

### **16.8.1 Exploratory Biomarker and Pharmacodynamic Analyses**

Biomarker and pharmacodynamic assessments, to include collection of peripheral blood, skin biopsies, and tumor biopsies, will be conducted in all patients and will evaluate potential predictive and/or prognostic biomarkers of response to treatment, including but not limited to: mutations; gene amplification and altered protein expression of members of the human EGFR family and other receptor tyrosine kinases; and downstream signaling mediators.

Biomarker analyses will be performed according to standard methodologies. Analyses will be described in the SAP.

### **16.9 Deviations from the Preplanned Statistical Analyses**

Any deviation(s) from preplanned statistical analyses defined prior to randomization of the first patient will be described in a protocol amendment and/or in the SAP and/or in the final CTR, as appropriate.

### **16.10 Interim Analysis**

**As of Amendment 5:** Due to the Sponsor's decision to discontinue the trial (effective 20Dec2018), only clinical safety-related analyses will be conducted. The planned interim analyses as detailed below will not be performed.

Per study design, tumor shrinkage will be evaluated at the end of Stage 1 and Stage 2. No other interim analysis is planned.

18 APPENDICES

Appendix 1 Performance Status Evaluation

Table 9: Measures of Performance Status				
Percent	KARNOFSKY Performance Status Description 		Level	Eastern Cooperative Oncology Group (ECOG) Performance Status Description 
100	Normal; no complaints, no evidence of disease		0	Normal activity
90	Able to carry on normal activity; minor signs or symptoms of disease			
80	Normal activity with effort; some signs or symptoms of disease		1	Symptoms but ambulatory
70	Cares for self; unable to carry on normal activity or do active work			
60	Requires occasional assistance but is able to care for most needs		2	In bed < 50% of time
50	Requires considerable assistance and frequent medical care			
40	Disabled; requires special care and assistance		3	In bed > 50 % of time
30	Severely disabled; hospitalization is indicated although death is not imminent			
20	Very sick; hospitalization is necessary		4	100 % bedridden
10	Moribund; fatal processes progressing rapidly			
0	Death		5	Death

## Appendix 2 New York Heart Association Functional Criteria

Table 10: New York Heart Association Functional Criteria	
Class I	No limitation of physical activity. Ordinary physical activity does not cause undue fatigue, palpitation, dyspnea, or anginal pain.
Class II	Slight limitation of physical activity. Comfortable at rest, but ordinary physical activity results in fatigue, palpitation, dyspnea, or anginal pain.
Class III	Marked limitation of physical activity. Comfortable at rest, but less than ordinary physical activity results in fatigue, palpitation, dyspnea, or anginal pain.
Class IV	Unable to carry on any physical activity without discomfort. Symptoms of cardiac insufficiency or anginal syndrome may be present even at rest. If any physical activity is undertaken discomfort increases.

The Criteria Committee of the New York Heart Association. *Nomenclature and Criteria for Diagnosis of Diseases of the Heart and Great Vessels*. 9th ed. Boston, Mass: Little, Brown & Co; 1994:253-256

### Appendix 3 Clinical Adverse Events: Grading Scale

Table 11: Clinical Adverse Event Grading		
Severity	CTCAE*Grade	Definition
Mild	1	Awareness of symptom, but easily tolerated. Event is usually transient requiring no special treatment; does not interfere with usual status or activities
Moderate	2	Event may be ameliorated by simple therapeutic measures; may interfere with usual activities
Severe	3	Event results in temporary disability or incapacity; inability to perform usual activities; requires intervention
Life-threatening	4	Event requires immediate intervention; need for emergency treatment; patient is at risk of death at the time of the event
Fatal	5	Event resulting in the subsequent death of the patient

Note: In those cases where further definition of an event is provided by the CTCAE (v5), please refer to that document for grading and severity information.

\* <[https://ctep.cancer.gov/protocoldevelopment/electronic\\_applications/ctc.htm#ctc\\_50](https://ctep.cancer.gov/protocoldevelopment/electronic_applications/ctc.htm#ctc_50)>

## Appendix 4 Clinical Adverse Events: Determining Relationship to IMP

Table 12: Clinical Adverse Event Attribution	
NOT-RELATED	
This category applies to those AEs which, after careful medical consideration, are clearly felt to be due to extraneous causes (disease, environment, etc.) that are not-related to the administration of IMP.	
RELATED ( must have first 3 )	
This category applies to those AEs, which, after careful medical consideration, are felt to be related to the administration of the IMP. The relationship of an AE to the IMP can be considered related if:	

• It follows a reasonable temporal sequence from administration of the drug or drug levels have been established in body fluids or tissues.

• It could not be reasonably explained by the known characteristics of the patient's clinical state, environmental or toxic factors, or other modes of therapy administered to the patient.

• It disappears or decreases upon cessation of drug or reduction on dose (if applicable) and appears upon rechallenge.*

• It follows a known response pattern to the suspected drug.

	

Adapted from: Karch FE and Lasagna L. Adverse drug reactions: a critical review. *JAMA*. 1975 Dec 22; 234 (12):1236-1241.

\*There are exceptions when an AE does not disappear upon discontinuation of the drug, yet drug-relatedness clearly exists, e.g., 1) tardive dyskinesia, 2) fixed drug eruptions.

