### 9.1 Criteria for Treatment Discontinuation

Patients will be discontinued from further treatment with IMP in the event of any of the following:

1. Progressive Disease: Confirmed radiographically (and evaluated according to RECIST v1.1)

*Note: Patients receiving futuximab or modotuximab with documented PD at the EOC2 (or prior to the EOC2) will be offered the opportunity to crossover to receive Sym004 or will be discontinued from study.*

2. Clinical Progression: Treatment failure not meeting the criteria for PD, but considered by the Investigator to require treatment discontinuation (i.e., global deterioration characterized by worsening PS, weight loss, and/or worsening clinical symptoms). **Every effort will be made to obtain imaging studies at the time of clinical progression.**

3. Adverse Event including:

- Hepatotoxicity characterized by:
  - AST and/or ALT elevation  $> 3 \times$  ULN (or  $> 3 \times$  baseline if elevated at study entry due to hepatic involvement by tumor), with
  - total bilirubin  $\geq 2 \times$  ULN without initial findings of cholestasis (i.e., serum ALP  $< 2 \times$  ULN), and
  - No explanation for the above findings such as viral hepatic injury, preexisting or acute liver disease, or another drug or condition capable of causing the observed injury

*Adapted from: Hy's Law. Drug-induced liver injury: premarketing clinical evaluation. Guidance for Industry. U.S. Department of HHS, FDA, CDER, CBER, 2009*

- Any of the following AEs:
  - Need for more than 2 dose reductions (Arm A), or more than 1 dose reduction (Arm B or Arm C)
  - Grade 4 IRR
  - Grade 4 EGFR-associated dermatologic AE
  - Torsade de pointes arrhythmia or other life-threatening arrhythmias
- Any other AE or SAE considered by the Investigator to require treatment discontinuation

Note: AEs resulting in a patient's permanent discontinuation from study treatment, regardless of seriousness or relationship to IMP, MUST be reported promptly to the Sponsor (or designee).

In the event of Grade 3 treatment-related AEs that are self-limiting or manageable by supportive care or other therapy, the patient may continue in study if there is evidence of response, disease stabilization, or other clinical benefit, but must do so at a reduced dose of IMP (see **Section 8.2.3**). Patients may not be retreated until retreatment criteria are met (see **Section 6.7.1**).

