### 10.1 Definitions of Adverse Events

#### 10.1.1 Adverse Event

An AE is any untoward medical occurrence in a patient or a clinical investigation subject administered a pharmaceutical product and which does not necessarily have a causal relationship with this treatment. An AE can therefore be any unfavorable and unintended sign (including an abnormal laboratory finding), symptom, or disease temporally associated with the use of an IMP, whether or not considered related to the IMP.

Causality for an AE will be assessed as related or not-related to IMP. Any AE, regardless of causality, that also meets the seriousness criteria, will be reported as an SAE.

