### 10.2.1 Information to be Provided for Each AE

The Investigator must record all directly observed AEs and all AEs spontaneously reported by the patient. Information regarding the occurrence of AEs should be elicited through open-ended questioning of the patient, review of physical examination findings, and review of laboratory results or other safety information, e.g., ECGs.

All AEs that occur in patients during the AE recording period must be recorded/entered to the AE section of the CRF, whether or not the event is assessed as related to IMP. If the AE is serious, the SAE report forms must also be completed and submitted. Information to be provided for each AE term reported includes:

- **Diagnosis**

A diagnosis should be recorded, if possible. If no diagnosis is available, signs and symptoms should be recorded instead. For fatal AEs, death is an outcome of the AE. The cause of death (rather than the term “death”) should be recorded.

- **Severity**

The Investigator will use the CTCAE version 5\* to describe the severity of an AE. If the severity of an AE is not specifically graded by the CTCAE guidance document, the Investigator should use the general definitions of Grades 1 to 5 as per the following, and use his/her best medical judgment to describe the severity of the AE (**Appendix 3**):

- Grade 1: Mild
- Grade 2: Moderate
- Grade 3: Severe
- Grade 4: Life-threatening or disabling
- Grade 5: Death caused by the event

Changes in severity of AEs will be recorded.

Generally, an AE of CTCAE Grade 4 or 5 qualifies for SAE reporting to the Sponsor (or designee). However, a laboratory abnormality of Grade 4 does not need to be reported as an SAE, unless it meets one of the SAE criteria.

*\*See <[https://ctep.cancer.gov/protocoldevelopment/electronic\\_applications/ctc.htm#ctc\\_50](https://ctep.cancer.gov/protocoldevelopment/electronic_applications/ctc.htm#ctc_50)>*

- **Relationship to IMP/Causality**

The Investigator will attempt to assess causal relationship of the event to the IMP. Relatedness must be assessed and recorded within the initial report (CRF and SAE report form).

The causal relationship is an assessment of whether the event is related to the use of the IMP. It is not an evaluation of whether the event could hypothetically occur in the investigational patient population.

The causal relationship of an AE to the IMP will be rated using a 2-point causality scale (**Appendix 4**):

- Not-related
- Related

- **Outcome**

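### Table 12 requires reappearance on rechallenge for Related, with no waiver where the drug was not given again, so a first event with no other explanation can meet neither causality level

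*Protocol*

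**What the plan says.** Section 10.1.1 sets a two-level scale: "Causality for an AE will be assessed as related or not-related to IMP". Section 10.2.1 repeats it, refers to Appendix 4 for the definitions and fixes the timing: "Relatedness must be assessed and recorded within the initial report (CRF and SAE report form").

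In Appendix 4, Table 12, the Related category carries the instruction "must have first 3". The first two criteria are plausible timing and the absence of another reasonable explanation. The third is "It disappears or decreases upon cessation of drug or reduction on dose (if applicable) and appears upon rechallenge". A footnote is attached to that criterion: "There are exceptions when an AE does not disappear upon discontinuation of the drug". Not-related is kept for events that "are clearly felt to be due to extraneous causes (disease, environment, etc".).

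Section 9.1 ends treatment for, among other things, hepatotoxicity with "No explanation for the above findings such as viral hepatic injury, preexisting or acute liver disease, or another drug or condition" able to account for it, for Grade 4 infusion-related reactions (IRRs), for Grade 4 EGFR-associated dermatologic events, and for "Torsade de pointes arrhythmia or other life-threatening arrhythmias". It closes the list with a general entry for any other adverse event that the investigator judges to require stopping.

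**The concern.** The third criterion joins dechallenge to rechallenge with a plain conjunction. The qualifier about applicability comes before the rechallenge clause, next to cessation and dose reduction. The footnote excuses only events that fail to resolve after the drug is stopped. No text covers the case in which the drug was not given again, and that is the normal case when the event itself ends treatment.

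Because Not-related demands a positive finding of another cause, the two definitions leave a gap between them. At stake is an undetermined or inconsistent causality entry for some of the most severe events. Investigator causality is an input to the SUSAR decision (10.3.2). Where treatment continues, relatedness also enters the retreatment criteria (6.7.1) and the handling of Grade 3 treatment-related events (8.2.3). Table 12 carries no Amendment 5 exception, and safety is the only thing still evaluated under that amendment.

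**Working it through.** There is no figure in the plan to reproduce. The check is logical, with one small timing sum.

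**Definitions (Table 12).** Let C1 be plausible timing, C2 no other reasonable explanation, D dechallenge (where applicable), R reappearance on rechallenge, and X a clearly extraneous cause.
- Related = C1 and C2 and (D and R).
- Not-related = X.
- Required by 10.1.1 and 10.2.1: exactly one of the two for every event.

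**Case 1: first occurrence of the 9.1 hepatotoxicity.** Take C1 as met. C2 is met and X is false, because 9.1 itself requires that no other explanation exist. Treatment stops, so R is not observed. Related fails on R and Not-related fails on X: 0 of 2 levels fit.

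**Case 2: causality entry due before re-exposure.** The initial SAE report is due within 24 hours of awareness (10.3.1), and dosing is weekly, plus or minus 2 days (6.5.4.6).
- Nominal interval: 7 − 1 = 6 days.
- Next dose 2 days early: 5 − 1 = 4 days.
- Next dose 2 days late: 9 − 1 = 8 days.

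A first SAE noticed within about the first 6 days after a dose (4 to 8) therefore has its causality entry due before the next dose. R is unobserved at that moment. If X is also false, neither level fits at entry.

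**Case 3: de novo Grade 4 IRR.** Section 8.1.1.1 makes the investigator's attribution to the infusion part of the definition of an IRR. Section 8.1.1.3 allows no further IMP after Grade 4, so R is unmet and Table 12 withholds Related. Here the two passages contradict each other.

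**Case 4: other first events that end treatment or are fatal.** This covers a Grade 4 dermatologic event, torsade or another life-threatening arrhythmia, or a death. R is unmet if there was no earlier recurrence on redosing. Whether X holds depends on the patient: with a clear extraneous cause the event is Not-related and there is no gap.

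**Case 5: recurrence after redosing.** Infusions may continue after a lower-grade IRR (8.2.1.1), and dosing may resume after a delay (8.2.2.2; Appendix 7, Tables 24 and 25). If the event came back, R is met and the rechallenge clause blocks nothing.

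**Terminology.** Sections 10.3.1 and 10.4 speak of possibly and probably related events, terms that the 2-point scale does not contain.

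**The case against.** The strongest reply is that Table 12 guides judgement and is not a truth table. Its lead-in rests on what the investigator, after consideration, feels to be related. The footnote shows that its authors accepted Related with the third criterion unmet, and the applicability qualifier may have been meant for the whole bullet. A strict reading also makes most first SAEs unclassifiable at entry, which can hardly be intended. This is a good argument about intent, and most investigators would probably record Related. It does not remove the instruction that the first three criteria must hold, and the word order does not carry the waiver to rechallenge. A rule that must be overridden to give a sensible answer should be corrected.

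On the IRR, it can be said that if related to the infusion means related to the IMP, 8.1.1.1 already settles the entry, and if it means something else, Not-related is not excluded by definition. That stands, and it is why the IRR is put here as a contradiction between two passages and not as an event without a level.

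The parenthesis in 10.3.1 can be read as spelling out what related covers. That is fair for 10.3.1. It would then imply a broader notion of related than Table 12 allows, and 10.4 has no such wording.

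The objection on consequences stands almost in full. SAEs and treatment-stopping events are reported whatever their causality (10.3.1, 9.1). Follow-up under 10.2.2 has no relatedness condition. Later information can be reported (10.2.1, 10.3.1). The Sponsor alone determines SUSARs (10.3.2), and a Drug Safety physician reviews every SAE (12.2).

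**Conclusion.** Wrong as written; severity minor. Read literally, Table 12 gives no level to a first-occurrence event with no other explanation that ends treatment, or to one whose entry is due before any re-exposure. It also contradicts 8.1.1.1 for a de novo Grade 4 IRR. The conclusion assumes that the first three criteria are mandatory as stated and that no earlier recurrence on redosing was documented.

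The size cannot be expressed as a number of events. Two patients are treated, and their data are shown as profiles or listings (16.5).

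Four stronger inferences are tempting and are not supported:
- A reader might count the named adverse-event criteria in 9.1 and report the share that cannot be classified. Item 3 also has a catch-all entry, and such a fraction counts list entries, not events.
- A reader might infer that no treatment-ending event can be Related. Case 5 shows otherwise.
- A reader might take 8.2.4 as barring rechallenge altogether. It bars a return to a higher dose; 8.2.2.2 permits a restart at the same dose.
- A reader might infer systematic under-attribution. The text does not fix the direction of the error.

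**What to change.** 1. In Table 12, state that the dechallenge/rechallenge criterion applies only where dechallenge or re-exposure actually took place, and is otherwise not required for Related.
2. Make the two levels exhaustive, so that an event with plausible timing and no clear other cause has a level. This also brings Table 12 into line with the IRR definition in 8.1.1.1.
3. Reconcile the possibly and probably related wording in 10.3.1 and 10.4 with the 2-point scale.

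The cost is a few words in Appendix 4, 10.3.1 and 10.4, and in any CRF instruction that repeats them. The downside is that somewhat more adverse events may be classed as Related.
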